# 4.7. Efficacy Variables

Efficacy will be assessed through the following parameters: fasting TG, HbA1c, fasting glucose, liver fat content as measured by MRI-PDFF, and lipodystrophy hunger questionnaire outcomes.

# 4.7.1. Primary Efficacy Variables

The two primary endpoints of the study are:

- Percent change in fasting serum TG from baseline to week 12.
- Absolute change in HbA1c from baseline to week 12.

## 4.7.2. Secondary Efficacy Variables

The secondary endpoints include:

- Percent change in fasting serum TG from baseline to week 24.
- Absolute change in HbA1c from baseline to week 24.
- Change in fasting glucose from baseline to week 12.
- Change in fasting glucose from baseline to week 24.
- Percent change in liver fat (MRI-PDFF) from baseline to week 12.
- Percent change in liver fat (MRI-PDFF) from baseline to week 24.
- Change on the daily lipodystrophy hunger questionnaire from baseline to week 12.
- Change on the daily lipodystrophy hunger questionnaire from baseline to week 24.

Regeneron Pharmaceuticals, Inc.

Page 24 of 88

Protocol: R4461-PLD-20100

# 4.7.3. SBTP-specific Secondary Efficacy Variables

SBTP-specific secondary efficacy endpoints include:

- Percent change in fasting serum TG from week 12 to week 24.
- Absolute change in HbA1c from week 12 to week 24.
- Change in fasting glucose from week 12 to week 24.
- Percent change in liver fat (MRI-PDFF) from week 12 to week 24.

# 4.8. Safety Variables

Patient safety will be assessed through the collection of reported adverse events (AEs), clinical laboratory data, vital signs, physical examination, and ECG. Unless otherwise noted, the baseline value is defined as the last available value before the first dose of double-blind study treatment.

#### 4.8.1. Adverse Events Variables

The period of safety observation starts from the time when the patient gives informed consent and continues into the following periods:

- The pre-treatment period is defined from the day the ICF is signed to the time of the first dose of double-blind study treatment administration.
- The double-blind treatment-emergent adverse event (DB TEAE) period is defined from the time of the first dose of double-blind study treatment administration to the day of the last dose of double-blind study treatment administration + 112 days (16 weeks) for those patients not proceeding into SBTP, or up to the time of the first dose of SBTP study treatment administration for those patients proceeding into the SBTP.
- The single-blind treatment-emergent adverse event (SB TEAE) period is defined from the time of the first single-blind study treatment administration to the day of the last single-blind study treatment administration + 112 days (16 weeks).
- The post-treatment period is defined from the day after the end of the respective TEAE period to the last study visit.

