#### 1.2.4. Modifications from the Statistical Section in the Final Protocol

The content of this SAP reflects the content of the statistical section of Protocol R4461-PLD-20100 Amendment 1 with the following exceptions:

- Protocol Section 4. Endpoints: The definitions of endpoints are clarified in SAP Section 5.7 by replacing:
  - "elevated baseline fasting TG" into "screening TG"
  - "elevated baseline HbA1c" for defining subgroup into "screening HbA1c" to match HbA1c strata (screening HbA1c ≤7.0%, >7.0%)
  - "baseline leptin" for defining Cohort into "screening leptin"
- Protocol Section 11.3.2. Safety Analysis Set: Safety analysis set (SAF) is replaced with DB SAF and SB SAF as follows in SAP Section 3.2:
  - DB SAF includes all randomized patients who received any double-blind study drug.
  - SB SAF includes all the patients in the double-blind SAF who also received at least 1 study drug in the single-blind treatment period.
- Protocol Section 11.4.5.4. Treatment Compliance: Compliance % calculation is replaced with study treatment administration interval compliance in SAP Section 5.8.8.
- Protocol Section 11.4.3. Efficacy Analyses: The randomization strata per IVRS in the analysis models (eg, MMRM) are replaced with actual strata in SAP Section 5.7 to reflect the actual disease characteristic for statistical modeling.
- Protocol Section 11.4.3. Efficacy Analyses: Due to the early termination of the study and subsequent limited number of participants enrolled, only descriptive summaries

Protocol: R4461-PLD-20100

and line plots for fasting TG, HbA1c, fasting glucose, liver fat (MRI-PDFF), and Daily Lipodystrophy Hunger Questionnaire (DLHQ) over time will be provided by treatment group. Spaghetti plots for fasting TG, HbA1c, fasting glucose, liver fat (MRI-PDFF), and DLHQ will be provided for individual patient data across visits for the endpoints by treatment group if applicable.

Protocol: R4461-PLD-20100

Date: May 16, 2024

• SAP Section 7 Timing of Statistical Analyses: First Step Analysis and Second Step Analysis will not be performed.

# 1.2.5. Revision History for Statistical Analysis Plan Version 1

This is the original version of the SAP.

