**Table 1: Summary of Study Arms** 

		Arm 1	Arm 2	
Double- blind	Day 1 (IV loading dose based on weight)	Placebo IV	mg/kg mibavademab IV	
Treatment Period (DBTP)	Day 8 onwards (for 11 weekly maintenance doses)	Placebo SC QW	mg mibavademab SC QW	
Single- blind Treatment Period (SBTP)	Day 85 (IV loading dose based on weight)	■ mg/kg mibavademab IV followed by Placebo SC	Placebo IV followed by mg mibavademab SC	
	Day 92 (for 11 weekly doses)	mg mibavademab SC QW		
	Day 169 until week 40	Off-Drug Safety Follow-up		

The study event table is presented in Appendix 10.7.

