#### General common rules

All safety analyses will be performed, unless otherwise specified, using the following common rules:

- Safety data in patients who do not belong to the safety analysis sets (ie, exposed but not randomized) will be listed separately.
- Potentially Clinically Significant Values (PCSVs) or Potentially Clinically Significant Abnormalities (PCSAs) are defined as abnormal values considered medically important by the Sponsor according to predefined criteria/thresholds based on literature review and defined by the Sponsor for clinical laboratory tests, vital signs, ECG (PCSV version dated January 2009 [Appendix 10.4]).

Regeneron Pharmaceuticals, Inc.

Page 42 of 88

Protocol: R4461-PLD-20100

• PCSV criteria will determine which patients had at least 1 PCSV during the respective TEAE period, taking into account all evaluations including unscheduled or repeated evaluations.

Protocol: R4461-PLD-20100

Date: May 16, 2024

- The treatment-emergent PCSV denominator for a given parameter will be based on the number of patients assessed for that given parameter at least once during the respective TEAE period.
- All measurements, scheduled or unscheduled, fasting or not fasting, will be assigned
  to the Global Analysis Windows defined in Appendix 10.2 to provide an assessment
  for the screening visit through follow-up visit time points.
- For quantitative safety parameters including central laboratory measurements and vital sign scores, descriptive statistics will be used to summarize observed values and change from baseline values by visit.
- Unless otherwise specified, in the case of multiple assessments within an analysis
  window, the assessment closest to the protocol planned visit study day will be used in
  analysis.

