#### **5.8.1.** Adverse Events

In general, the primary focus of AE reporting will be on TEAEs summarized in respective TEAE period, specifically the DBTP and SBTP.

If an AE onset date (occurrence, worsening, or becoming serious) is incomplete, an imputation algorithm will be used to classify the AE as pre-treatment, treatment-emergent, or post-treatment. The algorithm for imputing date of onset will be conservative and will classify an AE as treatment-emergent unless there is definitive information to determine pre-treatment or post-treatment status. Details on classification of AEs with missing or partial onset dates are provided in Section 6.3.

Adverse event incidence tables will present the number (n) and percentage (%) of patients experiencing an AE by SOC and PT. In addition, incidence tables by SOC and PT will be provided for all TEAEs, serious TEAEs, and TEAEs leading to permanent treatment discontinuation. Multiple occurrences of the same event in the same patient will be counted only once in the tables. For tables presenting severity of events, the worst severity will be chosen for patients with multiple instances of the same event. The denominator for computation of percentages is the respective safety analysis set within each treatment group.

AE incidence tables will present data by SOC and PT and summarize the number (n) and percentage (%) of patients experiencing an AE.

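### SAP 4.8.1 counts AEs and PCSVs over nominal windows of 84 to 189 days with no adjustment for time at risk, so double-blind and single-blind percentages are not comparable

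*SAP*

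**What the plan says.** SAP 4.8.1 starts the double-blind TEAE period at the first double-blind dose. It gives two ends: last double-blind dose plus "112 days (16 weeks) for those patients not proceeding into SBTP, or up to the time of the first dose of SBTP" treatment. The single-blind TEAE period runs "from the time of the first single-blind study treatment administration to the day of the last single-blind study treatment administration + 112 days". SAP Tables 17 and 18 repeat both definitions.

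On counting, SAP 5.8.1 says: "The denominator for computation of percentages is the respective safety analysis set within each treatment group". The general rules in SAP 5.8 say: "PCSV criteria will determine which patients had at least 1 PCSV during the respective TEAE period"; the PCSV denominator is the number of patients assessed at least once in that period. No visible output uses person-time, a time-to-event summary or a common time cut. SAP 5.8 presents the double-blind and single-blind tables separately and descriptively, the latter by double-blind arm and for all patients.

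Protocol 11.4.5.1 differs. Its on-treatment period ends 7 days after the last dose, and follow-up is one of its separate TEAE summaries. SAP 1.2.4, which lists the departures from the protocol's statistical section, does not mention the move from 7 to 112 days.

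**The concern.** A patient-count percentage rises with the length of time over which patients are watched. Here that length varies in two ways.

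- **Within the double-blind column.** Patients who enter the single-blind period contribute about 12 weeks. Patients who do not can contribute up to 27 weeks, much of it off drug. One percentage mixes the two.
- **Between periods.** The single-blind column folds up to 15 to 16 off-drug weeks into a 12-week dosing period. The double-blind column of a continuing patient has no such tail.

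A reader who sets Arm 1's placebo column beside its mibavademab column, or the double-blind placebo column beside the single-blind columns, will tend to see more events in the later column even if the drug does nothing. SAP 1.2.4 reports early termination and limited enrollment, so one or two patients with long windows can visibly move a percentage.

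**Working it through.** **Inputs.** Dosing days come from SAP Table 1: Day 1 infusion, then "Day 8 onwards (for 11 weekly maintenance doses"), so double-blind doses fall on Days 1, 8, ..., 78. The first single-blind dose is on Day 85, followed by 11 weekly doses on Days 92 to 162. The tail is 112 days (SAP 4.8.1). Days are nominal; visit windows of ±3 days are ignored.

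**The plan's own figure.** 16 weeks × 7 = 112 days, as stated. The documents do not give total window lengths.

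**Window lengths (elapsed days).**

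| Window | SAP rule | Protocol + 7 days, applied per period |
|---|---|---|
| Double-blind, continuing | 85 − 1 = 84 | 78 − 1 + 7 = 84 |
| Double-blind, not continuing, Day 1 dose only | 0 + 112 = 112 | 0 + 7 = 7 |
| Double-blind, not continuing, full course | (78 − 1) + 112 = 189 | 78 − 1 + 7 = 84 |
| Single-blind, Day 85 dosing only | 0 + 112 = 112 | 0 + 7 = 7 |
| Single-blind, full course | (162 − 85) + 112 = 189, ending Day 274 | 162 − 85 + 7 = 84 |

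The ratios to 84 days are 112/84 = 1.33 and 189/84 = 2.25. The off-drug part of the full single-blind window is 274 − 162 = 112 days (16 weeks) from the last dose, or 274 − 169 = 105 days (15 weeks) after the on-treatment period ends.

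**Size between periods (illustration).** Assume a constant hazard and no drug effect. Incidence over w days is 1 − (1 − p)^(w/84), where p is the 84-day incidence. For w = 189:

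- p = 10%: 1 − 0.90^2.25 = 21%
- p = 20%: 1 − 0.80^2.25 = 40%
- p = 40%: 1 − 0.60^2.25 = 68%

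**Size between arms, double-blind (illustration).** Suppose one arm all continues and a share q of the other does not. The spurious shift is q × [1 − (1 − p)^(w/84) − p]. The documents give neither q nor p, so I take both from 10% to 30%.

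- w = 112: from 0.10 × (0.131 − 0.10) = 0.3 points to 0.30 × (0.378 − 0.30) = 2.4 points.
- w = 189: from 0.10 × (0.211 − 0.10) = 1.1 points to 0.30 × (0.552 − 0.30) = 7.6 points.

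If non-continuation is equal in both arms, and the hazards are equal, the shift is zero.

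**Laboratory draws.** From the schedule of events, post-baseline hematology and chemistry samples number 6 in the double-blind window (Days 8, 22, 43, 57, 71 and predose 85) and 10 in the full single-blind window (Days 92, 106, 120, 127, 141, 155, 169, 197, 225, 253). Cut at Day 169, the single-blind count is 7, so the contrast becomes 6 v 7.

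**The case against.** The case against has real force on several points.

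- **The randomized comparison.** A reader might infer that the double-blind arm comparison is biased because the study stopped early. The documents do not support that. The same rule applies to both arms, and every continuing patient has 84 days. SAP 1.2.4 says only "Due to the early termination of the study and subsequent limited number of participants enrolled"; it does not say that enrolled patients missed the single-blind period, or that this differed by arm.
- **Window length in place of drug effect.** A reader might infer that the percentages reflect window length and not the drug. They reflect both.
- **Windows are ceilings.** Patients may withdraw at any time and are only asked to return, so a patient lost early is watched for less than the nominal window. It cannot be said that early stoppers are in fact followed longer than completers.
- **No planned contrast.** The SAP specifies no safety comparison of placebo period against drug period, and no inferential testing. By-visit laboratory and vital-sign summaries stop at last dose + 14 days and are unaffected.
- **Favourable arithmetic.** A constant hazard carries dosing-period risk through the off-drug weeks, although infusion and injection-site reactions cluster around dosing. A reader might also turn 6 v 10 draws into a PCSV excess at a fixed risk per draw. That needs independent draws within a patient, and repeated laboratory values are correlated, so I put no percentage on it.
- **The tail has a reason.** Protocol 3.2.1 expects pharmacodynamic effects to last less than 16 weeks after the final dose.

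What remains is that descriptive percentages by arm and period are what readers compare. The exposure summaries in SAP 5.6.1 and 5.8.8 give dosing duration and do not recover time at risk. The reason for the tail supports collecting and showing those events. It does not support merging them into the treatment-period column.

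**Conclusion.** The point holds as a defect of presentation. The SAP's TEAE windows are nominally 84, 112 to 189 and 112 to 189 days, and AE and PCSV percentages over them carry no time adjustment. Double-blind and single-blind percentages are not comparable: with full dosing the window is 2.25 times as long, although dosing lasts 12 weeks in both. The double-blind percentage mixes unequal follow-up, and this distorts the arm comparison only if non-continuation differs by arm.

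The window lengths follow from the schedule. The incidence figures (10/20/40% becoming 21/40/68%; a shift of 0.3 to 7.6 points between arms) are illustrations that rest on a constant hazard, no drug effect, and assumed event and non-continuation rates. The protocol's rule would have given equal windows for full courses, and the departure from it is not listed. The change is worth making because it is cheap and removes a real distortion.

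**What to change.** 1. In SAP 5.8.1, 5.8.2, 5.8.4 and 5.8.5, add n (%) for the protocol's on-treatment period, applied to each treatment period: first dose to last dose + 7 days, or to the first single-blind dose if earlier. State that the predose Day 85 samples belong to the double-blind period and the Day 169 end-of-period samples to the single-blind period, so that neither is lost through a day count.
2. Report the follow-up period as its own column.
3. Use the on-treatment columns for any comparison of arms or periods.
4. For AEs and AESIs, also give patients with an event per 100 patient-weeks actually observed. The + 7 day rule leaves early stoppers with 7 to 84 days, so their time at risk still differs.
5. Keep the + 112-day counts as supplementary.
6. List the change from 7 to 112 days in SAP 1.2.4, with its reason.
7. Leave ECG (SAP 5.8.6) out of the restricted columns. The scheduled ECGs from Day 1 are on Days 1, 85 and 281, so no post-dose single-blind ECG falls in the on-treatment period.

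The cost is SAP wording and extra table columns; the rules use dose, event and visit dates that the study already records. The rates will be imprecise at these numbers and are easiest to read if the hazard is roughly constant.

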Baseline testing occurs in the screening period and the placebo run-in period (see Table 1). After baseline testing, patients in each cohort will be randomized 1:1 to study arm 1 (placebo in TP1 and REGN4461 in TP2) or study arm 2 (REGN4461 in TP1 and TP2), and stratified based on screening HbA1c (HbA1c \leq 7.0% or HbA1c \geq 7.0%) within each cohort.

On day 1, the first dose will be administered IV (mg/kg REGN4461 or placebo) and patients will be observed for at least 4 hours. Starting on day 8, patients will receive matched volumes of SC administered REGN4461 (mg QW) or placebo, respectively, once weekly for a total of 11 SC doses. Fasting blood draws will be taken every 2 weeks according to Table 2.

During the final 2 weeks of TP1, fasting blood draws will be performed weekly (weeks 10, 11, 12). The mean (geometric for TG and arithmetic for all other measures) of these 3 measurements will be taken as the end measure of TP1 and beginning measurement for TP2. Bioimpedance will be assessed during a mandatory in-clinic study visit (week 12). At the end of TP1, patients will undergo liver MRI and whole-body DXA.

12-week single-blind treatment period (TP2); Day 85 until week 24

On day 85 (week 12), patients will receive double-blind dosing in order to maintain blinding to study arm assignment and will then be observed for at least 4 hours:

- Study arm 1: IV loading dose of REGN4461 (mg/kg) followed by SC placebo;
- Study arm 2: placebo IV infusion followed by SC REGN4461 (mg).

Starting at week 13, REGN4461 (mg SC QW) will be administered in a single-blind manner to patients in both study arms (patient remains blinded to treatment allocation). Fasting TG and glucose measurements will occur every 2 weeks through week 20 (Table 2). During the final 2 weeks of TP2, fasting blood draws will be performed weekly (weeks 22, 23, 24). The mean (geometric for TG and arithmetic for all other measures) of these 3 measurements will be taken as the end measure of TP2. Bioimpedance will be assessed during the mandatory in-clinic visit (week 24). At week 24, patients will undergo liver MRI and whole-body DXA.

16-week off-drug safety follow-up period; Day 169 until week 40

This period will be used to monitor efficacy (glycemic, lipid parameters, daily lipodystrophy hunger patient reported outcome [PRO]), safety (hematology, chemistry, urinalysis, vital signs and AEs), PK and PD assessments as REGN4461serum concentrations decline.

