8. STUDY TREATMENTS

8.1. Investigational and Reference Treatments

The REGN4461 dose regimen for this study is mg/kg IV followed by doses of mg SC QW. Placebo product to match to REGN4461 is prepared in the same formulation without the addition of REGN4461. All administration of REGN4461 or placebo is to be performed by study staff and no self-administration of REGN4461 or placebo will occur.

Dosing Schedule:

• **Single-blind run in:** all patients will receive an IV placebo infusion on day -28, followed by placebo SC QW injections administered subsequently for 3 weeks starting on day -21.

• Treatment period 1:

- Study arm 1: IV placebo infusion on day 1 followed by SC QW injections of placebo for 11 weeks starting on day 8
- Study arm 2: IV REGN4461 (mg/kg) infusion on day 1 followed by SC injections of REGN4461 (mg QW) for 11 weeks starting on day 8

• Treatment Period 2:

- Study arm 1: IV REGN4461 (mg/kg) infusion followed by SC placebo on day 85, followed by SC injections of REGN4461 (mg QW) for 11 weeks starting on day 92
- Study arm 2: IV placebo followed by SC injection of REGN4461 (mg mg) on day 85, followed by SC injections of REGN4461 (mg QW) for 11 weeks starting on day 92

Investigational drug formulation and instructions on dose preparation are provided in the pharmacy manual for in-clinic visits and in the nursing manual for remote visits.

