- 16. Two DXA scans will be performed as follows: Screening DXA will be performed at either visit 1 or visit 2. The second DXA will be performed during the run-in period and can be performed from day -28 to day 1 prior to dosing of study drug. Two baseline liver volume and liver fat content MRI-PDFF scans will be obtained from day -28 to day 1 prior to dosing. These 2 MRI-PDFF scans must be performed on separate days at least 24 hours apart and up to a maximum of 28 days apart. Patients may be required to fast at least 5 hours prior to the scans.
- 17. DNA should be collected at visit 1, but can be collected at any visit after obtaining consent.

Table 2: Schedule of Events: TP1, TP2 and Off-Drug Follow up

Study Period			Dou	ble Bl	ind Tı	reatmo	ent Per	iod (TP1))				S	Single	e Blii	ıd Tı	reatn	nent I	Perio	od (T	`P2)			E O T / E T 12	Fo	ff-[name] Perio	y up	E O S
	In - Cli nic O ut pa tie nt vis it		In-	-Clinio	e Outp	patient	visit o	r Rei	mote	visit	t		I n- Cl ini c O ut pa tie nt vis it	:	In-C	linic	Outj	patie	nt visi	it or	Ren	note	visit		O		-Clin atient		t
Visit Number:	8	6	10	11	12	13	14	15	16	17	18	19	20	21	22	23	24	25	26	27	28	29	30	31	32	33	34	35	36
Day:	1	8	15	22	29	36	43	50	57	64	71	78	85	92	66	106	113	120	127	134	141	148	155	162	169	197	225	253	281
±visit window (d):		±3	±3	±3	±3	±3	±3	± 3	± 3	± 3	± 3	± 3	± 3	± 3	± 3	± 3	± 3	± 3	±3	± 3	± 3	± 3	± 3	± 3	± 3	± 7	± 7	± 7	± 7
Week:		1	2	3	4	5	9	7	8	9	10	11	12	13	14	15	16	17	18	19	20	21	22	23	24	28	32	36	40
Patient Disposition																													
Randomization ¹	X																												
Treatment																													
Administer Study Drug (REGN4461/Placebo) ² (IV)	X												X																
Administer Study Drug (REGN4461/Placebo) ² (SC)		X	X	X	X	X	X	X	X	X	X	X	X	X	X	X	X	X	X	X	X	X	X	X					
Concomitant Medications and Treatment	X	X	X	X	X	X	X	X	X	X	X	X	X	X	X	X	X	X	X	X	X	X	X	X	X	X	X	X	X

Study Period			Dou	ble Bl	ind Tı	reatmo	ent Per	iod (TP1))				S	Single	e Blir	nd Ti	reatn	nent F	Perio	od (T	P2)			E O T / E T 12	Fo	ff-[name] bllow Perio	y up	E O S
	In - Cli nic O ut pa tie nt vis		In-	-Clinio	: Outp	atient	visit o	r Rei	mote	visit	;		I n- Cl ini c O ut pa tie nt vis it		In-C	linic	Outp	oatie	nt visi	it or	Ren	ıote	visit		O		-Clin ntient	ic t visit	t
Visit Number:	∞	6	10	11	12	13	41	15	16	17	18	19	20	21	22	23	24	25	26	27	28	29	30	31	32	33	34	35	36
Day:	1	8	15	22	29	36	43	50	57	64	71	78	85	92	66	106	113	120	127	134	141	148	155	162	169	197	225	253	281

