**Table 9: Analysis Windows for Vital Sign** 

Visit Label	Targeted DBTP Study Day	Targeted SBTP Study Day	Analysis Window in DBTP Study Days	Analysis Window in SBTP Study Days
Screening	< Day 1	N/A	Measurement obtained prior to 1st study trt, and not defined as baseline visit	N/A
Baseline	Day 1	N/A	Measurement obtained closest to 1st study trt, while remaining prior to 1st study trt.admin	N/A
Week 1	8	N/A	Day 2 to Day 11	N/A
Week 2	15	N/A	12 to 18	N/A
Week 3	22	N/A	19 to 25	N/A
Week 4	29	N/A	26 to 32	N/A
Week 5	36	N/A	33 to 39	N/A
Week 6	43	N/A	40 to 46	N/A
Week 7	50	N/A	47 to 53	N/A
Week 8	57	N/A	54 to 60	N/A
Week 9	64	N/A	61 to 67	N/A
Week 10	71	N/A	68 to 74	N/A
Week 11	78	N/A	75 to 81	N/A
Week 12	85	N/A	82 to SB Day 1	N/A
Week 13	N/A	SB Day 8	N/A	SB Day 2 to 11
Week 14	N/A	15	N/A	12 to 18
Week 15	N/A	22	N/A	19 to 25
Week 16	N/A	29	N/A	26 to 32
Week 17	N/A	36	N/A	33 to 39
Week 18	N/A	43	N/A	40 to 46
Week 19	N/A	50	N/A	47 to 53
Week 20	N/A	57	N/A	54 to 60
Week 21	N/A	64	N/A	61 to 67
Week 22	N/A	71	N/A	68 to 74
Week 23	N/A	78	N/A	75 to 81
Week 24	N/A	85	N/A	82 to 92
FU- W5	Last study trt admin day + 35 days	Last study trt a	dmin day +15 days TO last study trt	admin day + 49 days
FU-W9	Last study trt admin day + 63 days	Last study trt ac	lmin day + 50 days TO last study trt	admin day + 77 days

Visit Label	Targeted DBTP Study Day	Targeted SBTP Study Day	Analysis Window in DBTP Study Days	Analysis Window in SBTP Study Days	
FU-W13	Last study trt admin day + 91 days	Last study trt admin day + 78 days TO last study trt admin day + 105 days			
FU-W17	Last study trt admin day + 119 days	Last study trt admin day + 106 days TO last study trt admin day + 126 days			

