#### **10.7.3.** Early Termination Visit

Patients who withdraw from the study will be asked to return to the clinic for 2 visits: an EOT/ET visit and an end of study visit. The EOT/ET visit should take place within 5 days of treatment discontinuation, if possible. A final end of study visit should take place with assessments 17 weeks after the last dose of study drug as described in Table 22.

Patients who have discontinued study drug but who remain in the study will enter the off-drug follow-up period (Table 22) after completing the early termination visit. In the off-drug follow-up period, patients will continue with monthly visits until 17 weeks after last dose of study drug. Each of these monthly visits will consist of safety assessments, including laboratory tests.

Sexually active patients who discontinue the study prematurely should be reminded to maintain highly effective contraceptive measures for 17 weeks after the last dose of study drug.

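### The SAP closes the treatment-emergent and PCSV period at last dose + 112 days, a week before the scheduled end-of-study visit, so closing-visit values obtained on schedule miss the PCSV incidence tables

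*SAP*

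**What the plan says.** **End of the period.** SAP section 4.8.1 closes the single-blind TEAE period at "the day of the last single-blind study treatment administration + 112 days (16 weeks"; Table 18 repeats this. The same 112 days closes the double-blind period for patients who do not enter the single-blind period (section 4.8.1, Table 17) and the concomitant-medication periods in section 4.3.

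**What depends on it.** SAP section 5.8, general common rules: "PCSV criteria will determine which patients had at least 1 PCSV during the respective TEAE period". Sections 5.8.4 to 5.8.6 apply this to laboratory, vital-sign and ECG incidence. By-visit laboratory and vital-sign summaries stop earlier, at last dose + 14 days. In section 5.8.6 that 14-day limit introduces the ECG analysis as a whole.

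**Schedule.** Protocol section 8.1 gives the single-blind weekly injections "for 11 weeks starting on day 92". Protocol section 6.1 describes a "16-week off-drug safety follow-up period; Day 169 until week 40". The day row of Protocol Table 2 ends "162 169 197 225 253 281": the last dosing visit, the end-of-treatment visit, three follow-up visits and the end-of-study visit.

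**The SAP's own placing of the closing visit.** In SAP Tables 8 to 11 the FU-W17 target is "Last study trt admin day + 119 days", with window "Last study trt admin day + 106 days TO last study trt admin day + 126 days".

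**Early withdrawals.** SAP section 10.7.3: "A final end of study visit should take place with assessments 17 weeks after the last dose of study drug". Protocol section 9.1.3 gives 16 weeks for the same visit.

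**After the period.** SAP section 4.8.1 defines a post-treatment period up to the last study visit, and sections 4.8.1.1 and 4.8.1.4 define post-treatment adverse events and deaths. The tables listed in sections 5.8.1 to 5.8.3 are of treatment-emergent events only.

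**The concern.** The 112 days equals the length of the off-drug follow-up, but it is counted from the last dose, and follow-up starts a week after that dose. The cut-off therefore falls inside the SAP's own window for the closing visit. Whether that visit's values enter the PCSV incidence tables then depends on whether the patient comes early.

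At stake is the last off-drug reading of laboratory tests, vital signs and weight. It is collected, but on schedule it cannot contribute to PCSV incidence, and the by-visit summaries, which stop at last dose + 14 days, do not recover it. ECG is the sharpest case. The ECG row in the schedule is marked on Day 1, Day 85 and at end of study only, and the Day 85 recording is meant to precede dosing. At nominal timing the single-blind ECG PCSV analysis would then have no scheduled ECG inside its period, unless the footnote equating the early-termination/end-of-treatment visit with end-of-study assessments adds one at week 24.

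Adverse events starting in the final week move to a class with no table listed.

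**Working it through.** **Inputs**
- First single-blind dose of the 11-week weekly series: Day 92 (Protocol 8.1)
- Start of the 16-week follow-up: Day 169 (Protocol 6.1)
- End-of-study visit: Day 281, ±7 days; dosing visits ±3 days (Protocol Table 2)
- TEAE/PCSV limit: last dose + 112 days (SAP 4.8.1, 5.8)
- FU-W17: target last dose + 119, window +106 to +126 days (SAP Tables 8 to 11)
- Distribution of actual visit days: not given; assumed below

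**Reproducing the plan's figures**
- Last dose: 92 + 10 × 7 = Day 162
- 112 / 7 = 16 weeks, as the SAP states
- FU-W17 target: 162 + 119 = Day 281, matching the schedule
- FU-W17 window: 162 + 106 = Day 268 to 162 + 126 = Day 288
- Follow-up: 169 + 112 = Day 281, so the 16 weeks run from Day 169

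**The gap**
- End of the period: 162 + 112 = Day 274
- End of study minus end of period: 281 − 274 = 7 days
- The allowed end-of-study days are 274 to 288; with the last dose on Day 162, only Day 274 itself is inside the period

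**Share of completers' end-of-study visits outside the period** (visit day > last-dose day + 112)
- Nominal timing: 281 > 274, so 100%
- Last dose on Day 162, visit uniform over 15 days: 14/15 = 93.3%
- Last dose also uniform over Days 159 to 165, independently: 15 + 15 + 15 + 14 + 13 + 12 + 11 = 95 of 7 × 15 = 105, so 90.5%
- Visits clustered near target (assumed truncated normal, SD 1 to 4 days for the visit and 1 to 2 days for the dose): 96% to over 99%

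**Early withdrawals, same 112-day limit**
- Final visit at +112 (Protocol 9.1.3): 0% outside at nominal timing; 7/15 = 46.7% if uniform over an assumed ±7 days
- Final visit at +119 (SAP 10.7.3): 100% outside at nominal timing; 14/15 = 93.3% on the same assumption

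**Adverse events.** After a Day 162 last dose, any onset on Days 275 to 281 is post-treatment. The visit-timing percentages do not apply to events. An event starting by Day 274 but first reported at the closing visit is still treatment-emergent, because SAP 4.8.1.1 classifies by when the event developed, worsened or became serious.

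**Effect of moving the limit** (share of completers' end-of-study visits still outside, both windows uniform)
- Last dose + 119: 49/105 = 46.7%
- Last dose + 126: 3 + 2 + 1 = 6 of 105 = 5.7% (0% with the last dose on Day 162)
- End at the end-of-study visit: 0%

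**The case against.** The strongest case is that 112 days is a choice. It is correctly converted to 16 weeks. Protocol section 3.2.1 expects pharmacodynamic effects to persist for less than 16 weeks after the final dose, and the protocol uses the same interval for contraception, pregnancy reporting and the early-withdrawal final visit. By defining a post-treatment period up to the last visit, the SAP accepts that some follow-up lies beyond the treatment-emergent period. The SAP period is also already far longer than the protocol's on-treatment period of last dose + 7 days (section 11.4.5.1).

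This stands as a reason for 16 weeks in general. It does not explain a cut-off inside the SAP's own closing-visit window, with no table listed for events that fall after it.

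Three stronger readings are tempting, and the documents do not support them:
- **That late adverse events are lost.** They are recorded to the end of the study, SAP section 4.8.1.1 says all are reported and described, and incomplete onset dates default to treatment-emergent. The defect is their class and the missing table.
- **That about 90% is a property of the plan.** It needs independent, uniform visit timing and covers completers only; on schedule the figure is 100%. SAP section 1.2.4 reports early termination with few participants, so the number of completers is unknown.
- **That closing-visit values vanish altogether.** The listings of PCSV measurements in sections 5.8.4 and 5.8.5 carry no stated period limit, and abnormal results meeting the protocol's reporting criteria are recorded as adverse events. The loss is from the incidence tables.

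**Conclusion.** The concern holds in this form. The single-blind TEAE and PCSV period closes on Day 274, seven days before the Day 281 end-of-study visit that the SAP itself places at last dose + 119 days. For completers on schedule, all end-of-study laboratory, vital-sign, weight and ECG values miss the PCSV incidence tables, and one of the four off-drug follow-up visits (Days 197, 225, 253 and 281) contributes nothing to them. Under the assumed visit distributions the excluded share is 90.5% or more.

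For ECG the loss may be the only scheduled single-blind recording after Day 85; this depends on how the end-of-treatment footnote is read. Extending the TEAE period would not be enough for ECG while the 14-day limit in section 5.8.6 stands. For early withdrawals the size is undetermined until Protocol 9.1.3 and SAP 10.7.3 are reconciled.

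SAP section 1.2.4 reduces the efficacy analyses after early termination but lists no such reduction for safety, so the PCSV tables are still planned. This is a correction that should be made; it does not threaten the study's main conclusions.

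**What to change.** - In SAP sections 4.3 and 4.8.1 and Tables 17 and 18, end the period at the end-of-study visit, or at last dose + 126 days (the FU-W17 upper limit) if there is no such visit. Apply this to the single-blind period and to the double-blind period of patients who do not enter the single-blind period. Change the post-treatment medication definition in section 4.3 to match.
- In section 5.8.6, align the last dose + 14 days limit so that end-of-study ECGs can enter the PCSV count.
- Reconcile the timing of the final visit for early withdrawals between Protocol 9.1.3 and SAP 10.7.3.

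**Cost.** No new data or patient procedures are needed. The 112-day rule recurs in several places and must be changed in each, and in the programs. A few more late events will count as treatment-emergent, and the post-treatment adverse-event class will be nearly empty for patients who have an end-of-study visit.
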